6.1 Subject Disposition, Completion Rate and Reasons for Discontinuation

Subject disposition will be summarized for the Randomized Sample by the treatment group, and by center.

Subject completion rate and reasons for discontinuation will be summarized for the Randomized Sample by treatment group.

6.2 Treatment Compliance

Based on the Investigational medicinal product (IMP) panel of the CRF, compliance in taking IMP is calculated by dividing the number of tablets/capsules taken by the total number of tablets/capsules the patients were scheduled to take during the study period. For lost-to-follow up patients, last IMP end date record will be used as the treatment end date.

6.3 Protocol Deviation

Protocol deviations will be summarized by center and type of deviation for randomized subjects by treatment group. A listing of protocol deviations will be provided. In addition, protocol deviations affected by the COVID-19 will be summarized. Listing of subjects with protocol deviations affected by the COVID-19 will also be provided.

7 Baseline Characteristics

7.1 Baseline Definition

For analyses of the double-blind treatment period data, baseline measurement is defined as the last available measurement prior to the first dose of double-blind IMP, scheduled at the Week 1 visit.

7.2 Demographic Characteristics

Baseline demographic characteristics include age, sex, race, ethnicity, height, weight, waist circumference, and body mass index (BMI). For the Randomized Sample, demographic characteristics will be summarized by treatment group.

Mean, range and standard deviation will be used to describe continuous variables such as age. Frequency distributions will be tabulated for categorical variables such as race.

7.3 Medical and Psychiatric History

A summary of medical, psychiatric, and borderline personality disorder history will be presented for the Randomized Sample (by treatment group and overall).

7.4 Neuropsychiatric Diagnosis

A summary of the MINI International Neuropsychiatric Interview (M.I.N.I.) will be presented for the Randomized Sample (by treatment group and overall). Summarized will be the number and percentage of patients who meet each diagnosis criteria, and number and percentage of patients with each primary diagnosis.

A summary of the Structured Clinical Interview for DSM-5 Personality Disorders (SCID-5-PD) will be presented for the Randomized Sample (by treatment group and overall). Summarized will be the number and percentage of patients who meet criteria of each personality disorder.

7.5 Baseline Psychiatric Evaluation

For the Randomized Sample, baseline psychiatric scale evaluation will be summarized by treatment group and overall. The mean, median, range and standard deviation will be used to summarize the assessments of: ZAN-BPD Total Score, Clinical Global Impression – Severity

8 Efficacy Analysis

For analysis _____, baseline is defined as the last available measurement prior to the first dose of double-blind IMP, scheduled at the Week 1 visit.

All efficacy analyses will be performed on the FAS for Enriched Subjects and on the FAS unless specified otherwise, with FAS for Enriched Subjects being primary. Statistical comparisons are based on 2-sided, 0.05 significance levels.

8.1 Primary Efficacy Endpoint

The primary efficacy endpoint is the change from baseline to Week 10 visit in the ZAN-BPD total score.

8.1.1 Primary Estimand

The primary estimand defining the treatment effect of interest in the trial uses the hypothetical strategy specified in the International Conference for Harmonisation (ICH) E9 (R1) Addendum. The objective of the primary analysis is to compare the efficacy of brexpiprazole versus placebo for the treatment of subjects with a diagnosis of BPD. The estimand, or target of estimation, following the hypothetical strategy is the pharmacological effect seen, had no withdrawals occurred. This hypothetical estimand is justifiable in this case, since the focus is on the pharmacological effect of the drug additional to non-specific effects. Subjects who withdraw from a symptomatic IMP treatment either could have lost their treatment effect, had the subjects not taken any other symptomatic medication after withdrawal, or could have their treatment effect been masked, had the subjects taken other symptomatic medication after withdrawal. This means that any observations taken after subjects stop IMP will most likely not contribute relevant information about the pharmacological effect of the drug. Due to this strategy, the last collected efficacy assessment after premature trial discontinuation will be done only once at the ET Visit. Every effort will be made to complete all of the ET evaluations prior to administering any additional medications for the treatment of BPD or other prohibited medications. In the case of terminal or lost to follow-up events no ET evaluations would be expected, and only scheduled assessments performed before such an event has occurred.

The primary estimand for this trial is defined by the following components:

- Target Population: FAS for Enriched Subjects
- Endpoint: Change from Baseline to Week 10 in the ZAN-BPD total score
- Intercurrent Events: Premature treatment discontinuation
- Measure of Intervention Effect: Difference in endpoint means between Brexpiprazole and Placebo arm.

The National Emergency Announcement concerning the coronavirus disease 2019 (COVID-19) pandemic was declared on March 13, 2020. The pandemic had a significant impact on many aspects of clinical trials. There are occasionally virtual visits (i.e., virtual assessments) and possibly early discontinuation of treatment directly or indirectly related to the pandemic. However, subjects were required to attend the screening, Day 0, Week 1, Week 10, and the end of trial visits in person (i.e., face-to-face). The details of trial conduct during the COVID-19 pandemic are described in the COVID-19 specific protocol addendum. Note that virtual visits in the pandemic environment will not be treated as an intercurrent event for the primary analysis. Subjects who drop out with a reason relating to the COVID-19 pandemic will be handled as they would have dropped out for another reason if the pandemic had not happened.

The hypothetical strategy of handling intercurrent events will be used to clarify the efficacy of the brexipiprazole had there be no occurrence of intercurrent events, regardless of being COVID-19 related or not. In other words, the estimand as described above will use the hypothetical strategy to address the treatment effect of interest that would be envisioned under the hypothetical setting of no occurrence of intercurrent events in the planned 12-week treatment period.

The estimator will be the Mixed Model Repeated Measurements (MMRM) estimate for treatment difference at Week 10, based on all observed case (OC) data until discontinuation from the trial. This reflects the chosen strategies for the identified intercurrent events. Details of the model are provided in the next section.

In this hypothetical strategy, the event of withdrawing IMP is considered MAR, and the primary endpoint of the trial could be considered as a combination of the responses of ontreatment completers at Week 10 and the imputation of the endpoint to Week 10 following the trend in each treatment group using the MMRM method for subjects who withdraw IMP during the trial. All data collected during the trial treatment period will be used for statistical analysis. For the primary efficacy analysis, the treatment effect will be estimated using the MMRM method described in Section 8.1.2. Under the MAR assumption, MMRM provides an unbiased estimate of treatment effect for the treatment period. Analyses with missing values

imputed by multiple imputation (MI) under MNAR, and other methods will be performed as sensitivity analyses.

It's assumed that the placebo effect is reduced in the FAS for Enriched Subjects comparing to the FAS.

8.1.3 Technical Computation Details for Primary Efficacy Analysis

The SAS code for the PROC MIXED procedure to carry out the above MMRM analysis with an unstructured variance covariance structure is illustrated as follows:

```
proc mixed;
class treatment center visit ADT_Status sex subjid;
model change=treatment center visit ADT_Status treatment*visit baseline*visit age*visit
sex*visit/s cl ddfm=kenwardroger;
repeated visit /type=un subject=subjid r rcorr;
lsmeans treament*visit / pdiff cl alpha=0.05 slice=visit;
run;
```

where baseline is the ZAN-BPD Total Score at baseline (Week 1 visit of the double-blind treatment period).

8.1.4 Sensitivity Analyses

8.1.4.1 Sensitivity Analyses for Missing at Random (MAR) Assumption

The mixed-model repeated measures (MMRM) assume data are missing at random (MAR), which is a reasonable assumption in longitudinal clinical trials¹. However, the possibility of "missing not at random" (MNAR) data can never be ruled out. As sensitivity analyses, pattern-mixture model^{2,3,4,5} and shared parameter model⁶ will be used to explore data missing mechanisms of MNAR and investigate the response profile of dropout reason. Pattern Mixture Models based on Multiple Imputation (MI) with mixed missing data mechanisms will be used to investigate the response profile of dropout subjects by last dropout reason under MNAR mechanism for the following 3 scenarios: 1) Dropout reasons due to either AE or lack of efficacy (LOE) as MNAR, 2) Dropout reasons due to either AE or LOE or subject withdrew consent as MNAR, 3) All dropouts as MNAR using both 1) Delta adjustment imputation method which is to departure from MAR assumption by progressively increasing the delta until conclusion from the primary analysis is overturned, and 2) Placebo-based imputation methods in which missing data for both placebo and drug group are imputed based on the imputation model derived from placebo data. If drug improved outcomes prior to dropout, this benefit is carried into subsequent imputed values, but will diminish over time in accordance with the correlation structure.

Traditionally the dropout mechanisms are divided into three types (Little, 1995): (1) Missing Completely at Random (MCAR), in which the probability of dropout doesn't depend on the observed data and the missing data; (2) Missing at Random (MAR), in which the probability of dropout depends on the observed data, and (3) Missing Not at Random (MNAR), where the probability of dropout depends on the missing data and possibly the observed data.

Most of MNAR methods (Diggle P, Kenward MG, 1994) have treated all observations with dropout as if they fall within the same dropout type. In practice, we would find that different dropout reasons may be related to the outcomes in different ways, for example, detailed dropout reasons for this study are: adverse event (AE), death, lack of efficacy (LOE), lost to follow-up, non-compliance with IMP, pregnancy, protocol deviation, withdrawal by subject, trial terminated by sponsor, site terminated by sponsor, physician decision, and other. Dropout due to an AE, death and LOE may lead to MNAR dropout. Subject withdrew consent may also lead to MNAR dropout. However, it is debatable whether a dropout caused by subjects withdrew consent is MAR or MNAR. Except AE, LOE, and subject withdrew consent, all the other dropout reasons may be assumed as either MCAR or MAR dropout. Missing data due to COVID-19 will also be assumed as MAR.

As sensitivity analyses for missing at random (MAR) assumption, analyses for missing not at random (MNAR) will be carried out. Pattern Mixture Models (PMM) based on Multiple Imputation (MI) with mixed missing data mechanisms will be used to investigate the response profile of dropout patients by dropout reason under MNAR mechanism for the following three scenarios:

- 1) Dropout reasons due to either AE or LOE as MNAR
- 2) Dropout reasons due to either AE or LOE or subject withdrew consent as MNAR
- 3) All dropouts as MNAR

Delta Adjustment Imputation Methods

This MNAR sensitivity analysis is to departure from MAR assumption by progressively increasing the delta until conclusion from the primary analysis is overturned. The delta is 0%, 10%, 20%, 30%, ..., of the expected treatment difference of 2.6 points and/or the observed treatment difference between Brex and Placebo from the primary analysis of MMRM model until conclusion of the primary analysis is overturned. That is, until the primary efficacy results will tip over with p-value ≥ 0.05 . When delta=0 it is MAR. When delta > 0 it is MNAR.

- 1) Using Monte Carlo Markov Chain (MCMC) methodology from PROC MI to impute the intermittent missing data to a monotone missing pattern;
- 2) Using a standard MAR-based multiple imputation approach from PROC MI to impute the monotone missingness data
- 3) For patients in the treated group and with a dropout reason of AE or LOE or subject withdrew consent, a delta will be added for all the values after the dropout time.
- 4) Using ANCOVA model in the primary analysis to analyze the completed data using PROC MIXED on the multiple imputed data
- 5) Obtaining the overall results using PROC MIANALYZE.

The details of the imputation model under the MI procedure and related SAS codes are provided in Appendix 4.

Placebo Based Imputation Methods

Similar to "Standard" multiple imputations, except parameters for imputation model obtained from only the placebo (control) group. Missing data for both placebo and drug group are imputed based on the imputation model derived from placebo data. If drug improved outcomes prior to dropout, this benefit is carried into subsequent imputed values, but will diminish over time in accordance with the correlation structure.

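### SAP 8.1.4.1 names death as a possible MNAR dropout reason, then omits it from MNAR scenarios 1 and 2 and from the delta step, so a brexpiprazole-arm death gets no delta

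*SAP*

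**What the plan says.** All of this stands in SAP section 8.1.4.1.

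- Death is a dropout reason of its own: "detailed dropout reasons for this study are: adverse event (AE), death, lack of efficacy (LOE), lost to follow-up", followed by the rest of the list.
- It is then grouped with AE and lack of efficacy (LOE): "Dropout due to an AE, death and LOE may lead to MNAR dropout".
- Three sentences later the remaining reasons are disposed of: "Except AE, LOE, and subject withdrew consent, all the other dropout reasons may be assumed as either MCAR or MAR dropout". Death is not among the exceptions.
- Scenario 1 is "Dropout reasons due to either AE or LOE as MNAR", scenario 2 is "Dropout reasons due to either AE or LOE or subject withdrew consent as MNAR", and scenario 3 is "All dropouts as MNAR". The section gives the three scenarios twice, with the same content.
- The delta method first imputes everyone under MAR: "Using a standard MAR-based multiple imputation approach from PROC MI to impute the monotone missingness data". Step 3 then adds the penalty: "For patients in the treated group and with a dropout reason of AE or LOE or subject withdrew consent, a delta will be added".

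**The concern.** The delta analysis asks how bad the unseen outcomes of informative dropouts must be before the primary result is lost. For that, the subjects who receive the delta must be those whose dropout the plan regards as informative. Here the plan names three such reasons and carries only two of them into the rules that a programmer will follow. Withdrawal of consent, which the SAP calls debatable, has a scenario that includes it. Death, about which the SAP voices no such doubt, has none before scenario 3.

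At stake is a clear and credible tipping-point analysis, not the primary result. If a death occurred on brexpiprazole, a reader of the report would see that it was exempt from the penalty. A correction made after unblinding would look post hoc.

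**Working it through.** **Step 1. Where death appears in section 8.1.4.1**

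| Place | Reasons treated as MNAR | Death |
|---|---|---|
| Sentence on MNAR reasons | AE, death, LOE | included |
| Sentence on exceptions to MCAR/MAR | AE, LOE, withdrew consent | omitted, so MCAR/MAR |
| Scenario 1 | AE, LOE | omitted |
| Scenario 2 | AE, LOE, withdrew consent | omitted |
| Scenario 3 | all dropouts | included |
| Delta step 3 | AE, LOE, withdrew consent | omitted |

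**Step 2. Step 3 against the scenarios.** Step 3 is the only step that adds delta, and its list does not vary by scenario. In scenario 1 it adds delta for withdrawn consent, which that scenario does not class as MNAR. In scenario 2 it matches the scenario, with death missing from both. In scenario 3 it leaves out death and every other reason outside the three named. Read literally, a brexpiprazole-arm death gets no delta in any scenario.

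**Step 3. What the subject gets instead.** The value is drawn under MAR, given the subject's own earlier scores. With equal SD at each visit, the expected move from the last visit to Week 10 is

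move = (further mean change in the arm) − (1 − ρ) × (subject's deviation from the arm mean).

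Assumptions not in the documents: SD 6.5 at each visit, ρ from 0.5 to 0.8, further arm change from 0 to −3 points. Negative means improvement.

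- At the arm mean: 0 to −3.0.
- One SD worse (+6.5): from 0 − 0.2 × 6.5 = −1.3 to −3 − 0.5 × 6.5 = −6.25.
- One SD better (−6.5): from −3 + 0.2 × 6.5 = −1.7 to 0 + 0.5 × 6.5 = +3.25.

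The imputed score often improves but need not.

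**Step 4. Size.** Inputs from SAP section 4: expected difference 2.6, SD 6.5, 100 evaluable subjects per arm, two-sided 0.05, 80% power. The plan's own figure reproduces: the normal approximation needs 99 per arm, and 100 per arm gives 80.7% power (80.4% with the t distribution).

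- Standard error of the difference, unadjusted: 6.5 × √(2/100) = 0.919.
- Shift in the brexpiprazole mean = deaths × delta / 100.
- One death, delta 2.6 (100% of the expected difference): 2.6/100 = 0.026 points. This is 0.026/2.6 = 1% of the expected difference and 0.026/0.919 = 2.8% of the standard error.
- Three deaths (assumed; the documents give no death rate), delta 2.6: 0.078 points.
- Outer bound, one death shifted by the full 36-point range of the scale: 36/100 = 0.36 points.

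A death counts here only if it falls after a first valid post-randomization ZAN-BPD score (otherwise the subject is outside the analysis set) and before the Week 10 score.

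**The case against.** The strongest reply is that the two sentences do not strictly collide. Both are permissive: one says what may lead to MNAR, the other what may be assumed MAR. The operative rules agree with each other in omitting death, and the primary estimand in SAP 8.1.1 is hypothetical, under which MAR for a death can be argued. That stands as a possible position, but the SAP does not state it. It says the opposite about death and gives no reason for the change.

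A second reply is that a fatal event could be recorded under AE and receive delta that way. Protocol 7.3.3 does list serious adverse events under AE, but it and SAP 8.1.4.1 both keep death as a separate reason. Neither gives a mapping rule, so the outcome would depend on coding.

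Three stronger readings are tempting, and the documents do not support them.

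- A reader might infer that a subject who dies is imputed as continuing to improve in the assigned arm. MAR imputation conditions on the subject's own scores and can show worsening. The placebo-based code in Appendix 4 selects by treatment and last visit, never by dropout reason, so it imputes a brexpiprazole-arm death from the placebo model.
- A reader might infer that the worst outcome gets the most favourable handling. In scenarios 1 and 2 death is handled like loss to follow-up, pregnancy, physician decision and the other unlisted reasons. Delta is confined to the treated group, so a placebo-arm death gets none with or without a correction.
- A reader might infer that only scenario 3 penalises a death. In the delta method as written, not even scenario 3 does so. In the placebo-based code, the scenario plays no part.

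The point about likelihood also stands. Protocol section 2 describes the population as prone to suicidal behaviour, but Protocol 5.2.2 excludes subjects at significant suicide risk or with a recent attempt. The expected number of deaths is unknown and may be zero.

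**Conclusion.** The inconsistency is real and confined to the delta-adjustment analysis and the wording of scenarios 1 and 2. Death is named as possibly MNAR and then receives no delta in the brexpiprazole arm. Because step 3 has a fixed list, the literal text also contradicts scenario 3, and that mismatch reaches beyond death. The primary MMRM, the testing hierarchy, the sample size and the placebo-based code as written are untouched.

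The effect is about 0.026 points per death at delta 2.6, assuming 100 evaluable brexpiprazole subjects. It grows in proportion to the number of deaths and to delta. This is a minor correction that is worth making before unblinding.

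**What to change.** In SAP 8.1.4.1:

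1. Add death to scenario 1 (AE, death or LOE) and to scenario 2 (those plus withdrew consent), in both places where the scenarios are listed.
2. Add death to the exceptions in the sentence that assigns the other reasons to MCAR or MAR.
3. Replace the fixed list in step 3 with a rule tied to the scenario: in the treated group, add delta to the dropout reasons classed as MNAR in the scenario being run. That is AE, death and LOE in scenario 1, those plus withdrew consent in scenario 2, and all dropouts in scenario 3.

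If the sponsor prefers to treat death as MAR in scenarios 1 and 2, the SAP should say why and remove death from the sentence on MNAR reasons. Step 3 still needs the scenario rule. With death listed beside AE, it no longer matters which of the two codes a fatal event receives.

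The cost is a few words in the SAP, one extra reason code and a scenario condition in the program. Sample size, alpha and the primary analysis do not change.

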8.1.4.2 Supplemental Analyses for Violation of Normality Assumption

The primary endpoint MMRM analysis is a maximum likelihood method that relies on normality assumption. Residual analyses will be carried out to examine model assumption.

In the case of gross violations of the normality assumptions, nonparametric van Elteren test⁷ (van Elteren, 1960) stratified by center will be performed to compare treatment effect at Week 10 on Multiple Imputation (MI) data. The van Elteren test is a generalized Cochran-Mantel-Haenszel (CMH) procedure useful for stratified continuous data in non-normal setting. It belongs to a general family of Mantel-Haenszel mean score tests. The test is performed via SAS procedure PROC FREQ, by including CMH2 and SCORES=MODRIDIT options in the TABLE statement. The stratification factor is trial center.

In addition, other methods that are robust to distributional assumption will also be performed to provide different views on the primary efficacy result, these include generalized estimating equations (GEE), weighted GEE (WGEE), and MI-robust regression⁹.

For MI-van Elteren test and MI-robust regression, imputation datasets will be generated with SAS MI procedure, each dataset will be analyzed, and then an overall estimate is derived with SAS MIANALYZE procedure.

8.1.4.3 COVID-19 Pandemic Related Sensitivity Analyses

On March 13, 2020, the national emergence concerning the COVID-19 pandemic was announced in the US. The following analyses will be performed on the FAS for Enriched Subjects and the FAS, respectively, to evaluate the sensitivity of the primary and key secondary analysis results to the impact of the pandemic. The same model (e.g., with the same set of explanatory variables and the response variable) as that for the primary efficacy analysis will be used for these analyses specified below. Of note, the definition of intercurrent

events and the strategy for handling intercurrent events are identical to that for the primary efficacy analysis.

- 1. An MMRM analysis excluding the virtual assessments based on the FAS for Enriched Subjects and the FAS, respectively.
- 2. An MMRM analysis using the non-COVID data set based on the FAS for Enriched Subjects and the FAS, respectively. The non-COVID data set consists of the OC data during the non-COVID treatment period. For each subject, the non-COVID treatment period starts from randomization and ends on the Week 12/ET date, the date before the first virtual assessment or the date before the first COVID-19 related protocol deviation, whichever occurs earlier. The non-COVID treatment period represents the time period when subjects did not have any COVID-19 related protocol deviations or virtual assessments during the double-blind treatment period.
- 3. An MMRM analysis based on the non-COVID Sample. The non-COVID Sample comprises those subjects in the FAS for Enriched Subjects (or FAS) who did not have any virtual assessments nor COVID-19 related protocol deviations.
- 4. To explore the impact of assessments before versus after the COVID breakout, a subgroup analysis for subjects who completed or discontinued from the study before March 13, 2020 and subjects who completed or discontinued from the study on or after March 13, 2020 will be performed. An MMRM analysis based on the FAS for Enriched Subjects and the FAS will be performed to the extent where data allow or the summary statistics will be provided.

In addition, demographics and baseline characteristics by subgroup of subjects with or without any virtual visits will be provided.

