Screening/Other: SCID-5-PD, Mini International Neuropsychiatric Interview (MINI) for Psychotic Disorders, medical history, psychiatric history (including BPD history and BPD therapy), urine drug screen/blood alcohol test, and urine pregnancy test.

Data Monitoring Committee: None

Statistical Methods:

In general, descriptive statistics will be provided for all efficacy and safety endpoints. Continuous variables will be summarized by tabulations of mean, median, range, and standard deviation (SD). Tabulations of frequency distributions will be provided for categorical variables. The change from baseline in the ZAN-BPD total score will be analyzed using a mixed-effect model repeated measures (MMRM) methodology with the unstructured variance covariance matrix. The model will include fixed class-effect terms for treatment, trial center, visit week, and an interaction term of treatment by visit week and include the interaction term of baseline values of ZAN-BPD total score by visit week as a covariate. Other continuous efficacy endpoints will also be analyzed using MMRM methodology.

[figure not shown]
Trial Duration:

Each subject in this trial is expected to participate in the following periods of the trial (approximate durations listed):

- Eligibility screening period (up to 21 days)
- Double-blind randomized treatment period (12 weeks)
- Post-treatment safety follow-up period (21 days; for subjects who do not enroll in the open-label extension trial)

Overall, the trial duration from first informed consent form signed to the final subject assessment is expected to be approximately 15.5 months.

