3.1 Study Design

This will be a 12-week, multicenter, randomized, double-blind, placebo-controlled trial of brexpiprazole in subjects diagnosed with BPD according to the Diagnostic and Statistical Manual of Mental Disorders, 5th edition (DSM-5) and confirmed by a valid diagnostic instrument (Structured Clinical Interview for DSM-5 Personality Disorders [SCID-5-PD]). See Figure 3.1-1 for a schematic of the trial design.

The trial will be organized as follows:

Screening Period: The screening period will begin after written informed consent has been obtained and will take place between Day -21 and Day -1 prior to enrollment. Eligible subjects are required to meet all inclusion criteria at both screening and the start including a total score of ≥ 12 on the Zanarini Rating Scale for Borderline Personality Disorder (ZAN-BPD). In addition, a score of ≥ 2 in at least 2 of the following 4 ZAN-BPD scale items will be required at screening and Day 0: 1) "inappropriate, intense anger or difficulty controlling anger" (hereafter referred to as inappropriate anger), 2) "transient stress-related paranoid ideation or severe dissociative symptoms" (paranoid ideation), 3) "affective instability due to a marked reactivity of mood" (affective instability), and 4) "impulsivity in at least other two areas that are potentially self-damaging" (impulsivity).

assigned to treatment with brexpiprazole 2 to 3 mg/day or placebo in a 1:1 fashion. Subjects will receive their assigned treatment during an 11-week, double-blind treatment period. The timing of the primary and key secondary endpoints will be blinded to the investigator; these endpoints will be assessed after 9 weeks of assigned treatment (Week 10). Subjects will continue treatment through Week 12 of the trial. The primary endpoint and the key secondary endpoint will be the change from baseline to Week 10 in the clinician administered ZAN-BPD total score and Clinical Global Impression Scale - Severity of Illness (CGI-S) score, respectively. Visits will occur at the end of Weeks 1, 2, 4, 6, 8, 10, and 12/early termination (ET).

[figure not shown]
Post-treatment (Safety) Follow-up Period: Subjects who do not continue treatment in the open-label extension trial will be followed up for safety reasons via telephone contact or in clinic visit 21 (\pm 2) days after the last dose of investigational medicinal product (IMP). This contact also applies to subjects who are withdrawn prematurely from the trial.

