10.1 Study Visit Windows

Study visit windows will be used to map visits using study day intervals. Observations at each scheduled visit and Early Termination will be assigned to Week 1, Week 2, Week 4, Week 6, Week 8, Week 10 and Week 12 visits based on their visit windows as shown in Table 10.1A. This visit window convention applies to tables and listings for all efficacy and safety scales (ZAN-BPD, CGI-S, CGI-I, PGI-S, PGI-C, SAS, AIMS and BARS). This derived study window variable will be named as DAY and will be footnoted. In listings, it will be listed along with the CRF study visit.

Table 10.1A shows classifications for study day intervals in the double-blind period. The variable "target day" is defined using the number of days since the start of double-blind dosing. The first day of double-blind dosing is defined as "Day 1".

If more than one observation falls within a particular study day interval, then the last observation within that interval is used. Evaluations occurring more than 7 days after the last double-blind dosing date will not be mapped into study visit windows, and will be excluded from the analysis.

Table 10.1A: Study Day and Visit Windows

Week	Target Day ^a	Study Day Interval ^a
2	7	2-13
4	21	14-27
6	35	28-41
8	49	42-55
10	63	56-69

12	77	70-84 ^b

^a Relative to the first day of IMP in the double-blind treatment period.

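### The pre/post-COVID split in SAP 8.1.4.3 item 4 uses end-of-study date, so among subjects whose planned treatment spans 13 March 2020 only dropouts enter the 'before' group (minor, cheap to correct)

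*SAP*

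**What the plan says.** SAP 8.1.4.3 lists four pandemic-related sensitivity analyses. The aim of item 4 is "To explore the impact of assessments before versus after the COVID breakout". It forms two sets of subjects: one subgroup analysis is "for subjects who completed or discontinued from the study before March 13, 2020", and the other covers "subjects who completed or discontinued from the study on or after March 13, 2020 will be performed". An MMRM on the FAS for Enriched Subjects and on the FAS "will be performed to the extent where data allow or the summary statistics will be provided". SAP 8.2 applies similar analyses to CGI-S.

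Items 1 to 3 use other rules, based on virtual assessments and COVID-related deviations. None of them changes the grouping in item 4.

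On length of treatment, SAP 3.1 states: "Subjects will receive their assigned treatment during an 11-week, double-blind treatment period". Table 10.1A puts Week 10, the primary time point, at target Day 63 and Week 12 at target Day 77, counted from the first double-blind dose. The protocol synopsis gives 12 weeks of double-blind treatment. SAP 4 assumes a 5% non-evaluable/dropout rate and about 240 randomised subjects.

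**The concern.** The grouping variable depends on whether and when a subject stops, which is an outcome after randomisation. Take two subjects first dosed on 1 February 2020. The one who withdraws on 1 March is placed in 'before', and the one who stays is placed in 'after'. They entered under the same conditions and differ only in dropping out.

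The rule also misses its stated aim for some completers. A subject rated at Week 10 (Day 63) on 5 March reaches Week 12 (Day 77) fourteen days later, on 19 March. That subject is labelled 'after' although the primary rating predates the cut.

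A difference between the two subgroups could therefore reflect their dropout mix rather than the pandemic. If stopping also differs by arm, the treatment comparison within a subgroup is partly selected on outcome. Estimation under missing at random does not fully repair this. It relies on dropouts and completers appearing in their natural proportions, and the split changes those proportions.

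**Working it through.** The plan gives no figure for these subgroups, so there is none to reproduce. The size has to be illustrated.

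**Who is affected.** Let T be the planned treatment length. Counting back from 13 March 2020, T = 11 weeks gives about 27 December 2019 and T = 12 weeks gives about 20 December 2019. Subjects starting earlier are all in 'before', and subjects starting on or after 13 March are all in 'after', whether or not they complete. Only those starting in between are sorted by dropout.

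**Inputs from the documents.** T = 11 weeks (SAP 3.1) or 12 (protocol synopsis); dropout d = 5%, N = 240 and SD 6.5 (SAP 4).

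**Assumptions.** Accrual is uniform over A = 48 weeks. This is close to the protocol's 15.5 months (67.4 weeks) less 3 weeks of screening, 12 of treatment and 3 of follow-up, which leaves 49.4. The cut falls c = 26 weeks into accrual, dropout times are uniform over T, and there is no pandemic effect. Dropout rates of 15% and 25% are also assumed.

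**Formulas**, in weeks of accrual, for c > T:
- Before: dropouts d(c − T/2); completers (1 − d)(c − T).
- After: dropouts d(A − c + T/2); completers (1 − d)(A − c + T).

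**Worked case, d = 5%, T = 11.**
- Before: 0.05 × 20.5 = 1.025 dropouts and 0.95 × 15 = 14.25 completers; share 1.025/15.275 = 6.7%.
- After: 0.05 × 27.5 = 1.375 dropouts and 0.95 × 33 = 31.35 completers; share 1.375/32.725 = 4.2%.

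| Dropout | T = 11: before / after | T = 12: before / after |
|---|---|---|
| 5% (SAP 4) | 6.7% / 4.2% | 7.0% / 4.2% |
| 15% (assumed) | 19.4% / 12.8% | 20.1% / 12.7% |
| 25% (assumed) | 31.3% / 21.7% | 32.3% / 21.5% |

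**Subjects involved.** The spanning cohort is 240 × T/48, which is 55 subjects (23%) for T = 11 or 60 (25%) for T = 12. Those placed in 'before' by dropping out number 240 × d × (T/2)/48. That is 1.4 to 1.5 subjects at 5%, 4.1 to 4.5 at 15% and 6.9 to 7.5 at 25%.

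**Earlier cut.** With c = 17 weeks, the shares are 9-10% against 4% at 5% dropout, and 39-42% against 22% at 25%.

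**Effect on the treatment difference: a rough bound.** At 5% dropout the 'before' group has 240 × 15.275/48 = 76 subjects (T = 11) or 240 × 14.3/48 = 72 (T = 12), so about 36 per arm at the lower end.
- Suppose all 1.5 sorted dropouts are in one arm and each differs by 5 ZAN-BPD points (assumed). The shift is 1.5 × 5/36 = 0.2 points, against a standard error of 6.5 × √(2/36) = 1.5.
- At 25% dropout and T = 12, the group has 240 × 15.5/48 = 77.5 subjects, or 38.75 per arm. With the 7.5 sorted dropouts split 5.0 to 2.5 between arms, the shift is (5.0 − 2.5) × 5/38.75 = 0.3 points, against a standard error of about 1.5.
- With equal dropout and equal deviation in both arms, the shift in the difference cancels.

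**Under a rule fixed at first dose.** Group membership no longer depends on stopping, so the expected dropout share is d in both groups.

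**The case against.** Item 4 is explicitly exploratory. It reduces to summary statistics if data are thin, sits outside the testing hierarchy in SAP 8.3, and stands beside three other pandemic analyses. Item 2 already works at assessment level, ending each subject's data before the first virtual assessment or COVID-related deviation. All of this stands, and it keeps the point minor.

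The end-date rule also has a merit: no subject in 'before' can have a study rating made after the outbreak. That stands too. The cost is that the purity is obtained by selecting on dropout, and 'after' still contains many pre-outbreak ratings from subjects who span the cut.

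Both analysis sets require at least one post-randomisation ZAN-BPD rating, so dropouts with no rating never enter. The shares above count all randomised subjects and may therefore be somewhat high.

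Three stronger readings might be inferred, and the documents support none of them:
- **Dropout differs grossly between the groups, such as 42% against 22%.** That needs 25% dropout and a cut 17 weeks into accrual. The documents give 5% and no first-randomisation date.
- **The pandemic conclusions or the primary result are biased.** The primary MMRM does not use this split, and the bound above is small against its standard error.
- **Item 3, the non-COVID Sample, needs the same correction.** Longer stays do give more chances of a virtual visit, but the documents give no frequency from which to size this. Item 2 is already specified for comparison, so no change to item 3 is asked for.

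**Conclusion.** The point holds as a minor one, limited to item 4. That the rule sorts spanning subjects by dropout follows directly from its wording and needs no assumption. The size does need assumptions: accrual pattern, position of the cut, and any dropout rate above 5%. At the planned 5% with a cut near mid-accrual, one or two of 240 subjects are sorted by dropout and the shares are about 7% and 4%. The gap widens with more dropout or an earlier cut. The within-subgroup treatment difference is little affected unless dropout is high and unequal between arms. The primary analysis, the sample size and the testing hierarchy are untouched.

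**What to change.** In item 4, classify each subject by whether the planned Week 10 date falls before, or on or after, 13 March 2020, whether or not the subject completed. The planned date is target Day 63 in Table 10.1A with the first double-blind dose as Day 1, that is, first-dose date plus 62 days. Use the same grouping for the corresponding CGI-S analysis.

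State the trade-off in the SAP: some ratings will lie on the other side of the cut from their subject's group. The subject rated at Week 10 on 5 March moves to 'before' but has a Week 12 rating on 19 March, which enters the MMRM. The subject first dosed on 1 February has Day 63 on 3 April and so stays in 'after', even if withdrawal on 1 March leaves only pre-outbreak ratings.

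The cost is a sentence or two of SAP text and one derived variable from a date already held. No new data are needed.
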